## 4. TRIAL PROCEDURES

### 4.1. Informed Consent

Prior to being enrolled in the clinical study, subjects must consent to participate after the nature, scope, and possible consequences of the clinical study have been explained in a form understandable to them and per the requirements in 21CFR Part 50.20. The written informed consent document is provided in *Appendix A* of this protocol. Subjects are free to withdraw consent at any time, irrespective of their initial consent.

After reading the informed consent document, the participant must personally sign and date the latest approved version of the informed consent form before any study specific procedures are performed. A copy of the signed consent document must be given to the subject. The original signed consent document will be retained by the investigator.

The investigator will not perform any exams or testing specifically required only for the clinical study until valid consent has been obtained.

Any use of the device without obtaining informed consent shall be promptly reported (no later than 5 working days) to the study sponsor and the IRB.

[figure not shown]
### 4.2. Blinding/Masking

Although it is not possible to blind the study subject or the investigator to the treatment group, weight measurements are to be performed by clinical staff who are blinded to the treatment group. Subjects will be instructed not to speak with weighing personnel and to not disclose if they are control or treatment arm.

### 4.3. Study Timeline

The study timeline is summarized in [Figure 1](#):

**Figure 1: Study Timeline**

#### 4.3.1. Screening and Eligibility Assessment

Screening will be conducted by the investigator or co-investigator and documented on the PI Intake form (*Appendix E2: CRF\_2 PI Intake*) and Screening Labs form (*Appendix E3: CRF\_3 Screening Labs*). Screening must occur no more than 30 days prior to implantation.

Screening will include the following:

1. Screening exam by investigator or co-investigator (*Appendix E2: CRF2\_PI Intake*). Includes Medical history, Current medications, Record contraceptive method for female subjects, Vital signs, Body Weight and Height, Physical exam, Evaluation of inclusion/exclusion criteria.
2. Sign Informed Consent Form (*Appendix A: Informed Consent*)
3. Dietician intake - Baseline body weight, height, ideal body weight, excess weight, BMI, (*Appendix E5: CRF5\_Dietician Intake*)
4. Laboratory tests\* plus EKG
5. Psychological evaluation (*Appendix E10: CRF10\_Consultation with Psychologist*)
6. Diabetic subject – follow up by provider or PI (*Appendix E11: CRF11\_Diabetic Patient Follow Up*)

\*Laboratory Tests (*Appendix E3: CRF3\_Screening Labs*) include:

CBC: Hgb, Hct, WBC, MCV, platelets

Chemistry panel: sodium, potassium, chloride, CO2, BUN, creatinine, glucose, SGOT/AST, SGPT/ALT, alkaline phosphatase, total bilirubin, total protein, albumin, total cholesterol, Fe/TIBC, B12, Folic Acid, 25-Hydroxy Vitamin D, TSH

Coag: Pro Time or INR, PTT

Urinalysis

HgbA1c (if diabetic)

H. Pylori Serology

Within 1 week of the screening tests, the PI will review the results and determine eligibility of the subject. The center will inform the subject of their results within 10 days of the tests. All potential subjects who pass the initial screening assessment must return for an additional visit within 7 days of the scheduled implantation procedure for the Pre-Implantation visit (*Appendix E4: CRF4\_Preimplantation Tests and Data*). This will include an assessment of the following:

- Urine pregnancy test (women of child-bearing potential)
- Medications List
- Weight (Note: This is the baseline weight that will be used for the endpoint assessments)

Subjects with a positive pregnancy test or who are taking medications listed in the exclusion criteria will be excluded from the study at this time, and will be considered to be screening failures.

Investigators must retain study documentation for all patients who have been screened, regardless of whether or not they are accepted as study subjects.

#### **4.3.2. Randomization**

Subject will be randomly assigned to treatment or control group with a 2:1 allocation as per a computer generated randomization schedule using variable block randomization using the following stratification factors: treatment center and then by BMI (<35 kg/m^2 vs. ≥ 35 kg/m^2). The randomization schedule will be created by the study statistician, and will remain confidential.

Subjects will not be informed of their randomization status until the day of implantation. Subjects randomized to the treatment group will proceed to implantation, and subjects randomized to the control group will proceed to an appointment with a dietician.

#### **4.3.3. Trial Intervention**

##### **4.3.3.1. Control Group**

The control group will be provided with dietary counselling monthly during the 32-week study. The first dietician visit will commence on the day of randomization. A diet plan will be reviewed with each subject and will be adjusted according to the needs of each subject (*Appendix C: Diet and Exercise Plan*). In addition, exercise counselling will be given by the dietician with specific exercises detailed (*Appendix D: Physical Exercise Program*). The progressive exercise plan will have 3 phases that are gradually phased in over the 32-week follow-up period.

##### **4.3.3.2. Treatment Group**

###### **4.3.3.2.1. Implantation**

The Spatz3 balloon is implanted in an outpatient setting via upper endoscopy under conscious sedation. The subject fasts from midnight the night prior to the procedure. Conscious sedation will utilize a combination of Propofol, Midazolam, and a narcotic such as Fentanyl. A standard upper endoscopy is performed to rule out contraindicating findings such as a large hiatal hernia (>2 cm), esophagitis of any degree, erosive gastritis or ulceration of the stomach or duodenum.

Prior to implantation the balloon is prepared as follows: the bands are removed using “band-off” pull strings; the valve is secured to the white catheter using “valve-hold”, the Spatz3 balloon is secured to the endoscope by the insertion facilitator and finally the extension tube is connected to the valve. The scope with balloon secured to its side is passed into the throat and continues into the esophagus and stomach. Upon arrival in the stomach a retroflex maneuver confirms the presence of the balloon in the stomach and below the gastro-esophageal junction. The scope is then straightened and the balloon is inflated by connecting the 3-way stopcock at the proximal end of the extension tube to the provided 60 ml syringe and a 500 ml bag of Normal Saline. The 500 ml bag of Normal Saline will be injected with 2 cc of 1% Methylene Blue.

The balloon is initially inflated according to the following criteria:

- Initial balloon volume for subjects with height < 64 inches;
  - 450 ml (without history of GE reflux)

- 400 ml (with history of GE reflux)
- Initial balloon volume for subjects with height  $\geq$  64 inches;
  - 550 ml (without history of GE reflux)
  - 500 ml (with history of GE reflux)

After final balloon volume is achieved, the extension tube is pulled out of the mouth and the valve is disconnected from it and replaced with a cap. The capped valve is released and allowed to return to its position behind the balloon. The endoscope pushes the valve and catheter below the GE junction and the endoscope is then removed.

#### **4.3.3.2.2. Diet and Exercise**

The Treatment and control group will be provided with dietary counseling monthly during the 32-week study and the 24 week follow up. The first dietician visit will commence on the day of randomization. A diet plan will be reviewed with each subject and will be adjusted according to the needs of each subject (Appendix C: Diet and Exercise Plan). In addition, exercise counseling will be given by the dietician with specific exercises detailed (Appendix D: Physical Exercise Program). The progressive exercise plan will have 3 phases that are gradually phased in over the 32-week follow-up period.

#### **4.3.3.2.3. Medications**

All treatment arm subjects will receive the following oral medications for the implantation and upward adjustment procedures:

- Aprepitant (Emend) [implantation procedure only] 125 mg immediately prior to or 1 hour after the procedure, 80 mg the morning after the procedure and another 80 mg two mornings after the procedure.
- Ondansetron 8 mg will be taken every 6 hours starting 1 hour after the procedure for 12 tablets (3-4 days);
- Hyoscyamine 0.125 mg prn for abdominal pain or spasm 1-2 tablets every 4 hours sublingually (maximum 12 tablets/ 24 hours)
- Percocet 10 mg will be provided for subjects who have abdominal pain that is not relieved by Hyoscyamine.
- A PPI (proton pump inhibitor such as Nexium 20 mg, Protonix 40 mg or Prevacid 30 mg) will be taken daily for the entire 8 months to reduce acid in the stomach. This helps preserve the silicone and also controls acid reflux symptoms, should they arise.
- Probiotic, Acidophilus, 8-10 Billion CFU will be taken once daily for the 8-month period.

During the 8-month implantation period, different symptoms may arise such as constipation, nausea, vomiting, bloating, abdominal pressure, heartburn, and diarrhea. These can be treated as discussed below.

Constipation is expected in the first week after implantation. It generally resolves after oral intake increases in the first 2 weeks. If it persists, standard treatments such as a teaspoon of mineral oil daily, Milk of Magnesia, or Miralax (OTC med) 17 gram+ 8 oz water twice daily.

Nausea and/or vomiting or bloating or abdominal pressure can be treated with metoclopramide – 10 mg orally up to 4 times in 24 hours.

Heartburn can be treated by increasing the PPI medication to twice daily; addition of antacids such as Maalox, Mylanta, Gaviscon – 30 ml or 2 tablets every 3-4 hours; or addition of Sucralfate suspension 1,000 mg 4 times daily

Diarrhea is expected in about 20-25% of patients and is due to a mild case of bacterial overgrowth in the stomach and small intestine. Should diarrhea develop, the probiotic Acidophilus will be increased to 4 pills daily for 4 days and during those 4 days the PPI will not be taken. In the event those measures do not alleviate the diarrhea, treatment with Metronidazole 500 mg 3 times daily for 5 days will commence - generally the diarrhea improves on the first day of treatment. Some subjects have recurrence and require repeat treatment.

Foul-smelling belches may occur in 20% of subjects as a result of continuous administration of daily PPI medications in combination with balloon induced delayed gastric emptying. At the discretion of the investigator, these subjects may benefit from a 3-day holiday from the daily dose of PPI. No more than two such PPI holidays should be prescribed in any month. Gastro-esophageal reflux symptoms can be managed by use of antacids at a dose of 30 ml PO QID prn during the 3-day holiday.

For subjects intolerant to PPI medications (headache, diarrhea, abdominal pain, nausea, vomiting), the investigator will have the option of discontinuing the PPI and substituting any H2 Blocker medication at a twice daily dosing (Ranitidine 150 PO BID; Famotidine 20 mg PO BID ; Nizatidine 150 mg PO BID).

#### 4.3.3.2.4. Gastric Ulcers and H. Pylori treatment

For the purposes of this study, a *gastric ulcer* is defined as a gastric lesion  $\geq 5$ mm in diameter with unequivocal depth by endoscopy.

A gastric ulcer is defined as *endoscopically significant* if it is  $\geq 3$ cm in length and  $\geq 1$ cm in width. Dimensions should be confirmed by capturing clear images with an accessory of known dimensions next to the lesion.

Gastric ulcers/gastritis require biopsy for H.pylori (urease test) and treatment with “triple” regimen for 14 days if positive.

- PPI BID
- Amoxicillin 1 gram PO BID
  - (Pcn allergic – substitute metronidazole 500 mg PO BID)
- Clarithromycin 500 mg PO BID

Blood hemoglobin will be monitored during scheduled or unscheduled endoscopies in patients who have ulcers or report signs of upper GI bleeding (hematemesis or melena).

#### 4.3.3.2.5. Adjustments

##### 1. Adjustments for Intolerance

The PI may make an adjustment to the balloon volume at any time if the patient has symptoms of continued nausea, vomiting, uncontrolled GE reflux or abdominal pain in spite of conservative symptomatic treatment.

For intolerance that continues more than 7-10 days beyond the first 5 days after implantation or that occurs at any time during the 8 months, the investigator should:

- remove 150 ml from balloon (when initial volume is 450-550ml)
- remove 100 ml from balloon (when initial volume is 400ml)

The final volume should not be reduced below 300ml. If medications and balloon volume down adjustment do not alleviate the intolerance, the balloon should be extracted.

## 2. *Unscheduled endoscopy*

An unscheduled endoscopy may be performed at any time at the discretion of the investigator.

The following procedures will be applied to subjects who present with endoscopic findings based on an unscheduled endoscopy.

### Gastric Ulceration

Subjects who present with an endoscopically confirmed gastric ulcer will be treated as follows:

- **Ulcers whose smallest dimension (S) is  $\geq 2$ cm, or if there are any stigmata of increased risk of bleeding, such as visible vessels or clots**

The balloon should be extracted. Biopsy for H.pylori will be performed and treatment prescribed if positive.

These subjects should be treated with the following regimen: with sucralfate 1,000 mg PO Qid, and PPI medication twice daily for 3 months, followed by endoscopic evaluation after 3 months to confirm healing.

- **Ulcers whose smallest dimension (S) is  $\geq 1$  cm and  $< 2$  cm**

The balloon volume should be decreased by 150 ml (or 100 ml if starting volume is 400 ml) and subjects should be treated with the following regimen: sucralfate 1,000 mg PO Qid and increasing PPI medication to twice daily for 2 months. A biopsy for H.pylori will be taken and treatment prescribed if positive.

Endoscopic follow up will be performed at 8 weeks and if not healed at 8 weeks, an additional endoscopy at 16 weeks to confirm healing.

- At the 8-week follow-up, if signs of healing defined by a 25% reduction in either length or width are not observed, then the balloon should be extracted.
- At the 16-week follow-up, if signs of healing defined by a 50% reduction from baseline in either length or width are not observed, then the balloon should be extracted, and healing confirmed at follow up endoscopy 2-3 months after extraction.

These subjects will not undergo adjustment at  $18 \pm 4$  weeks.

- **Ulcers whose largest dimension is  $\geq 1$  cm and whose smallest dimension (S) is  $< 1$  cm.**

The balloon volume should be decreased by 150 ml (or 100 ml if starting volume is 400 ml) and subjects should be treated with the following regimen: sucralfate 1,000 mg PO Qid and increasing PPI medication to twice daily for 3 months. A biopsy for H.pylori will be taken and treatment prescribed if positive.

Endoscopic follow up will be performed at 12 weeks and if not healed at 12 weeks, an additional endoscopy at 20 weeks to confirm healing.

- At the 12-week follow-up, if signs of healing defined by a 25% reduction in either length or width are not observed, then the balloon should be extracted.
- At the 20-week follow-up, if signs of healing defined by a 50% reduction from baseline in either length or width are not observed, then the balloon should be extracted.

These subjects will not undergo adjustment at 18±4 weeks.

These recommendations are summarized in the following table:

		L – Largest Dimension (cm)				
		0 – 0.5	0.5 – <1.0	1 – <2	2 – <3	≥ 3
S - Smallest Dimension (cm)	0 – 0.5	Not ulcer	Increase Medication	Decrease balloon volume Follow-up 12 and 20 weeks	Decrease balloon volume Follow-up 12 and 20 weeks	Decrease balloon volume Follow-up 12 and 20 weeks
	0.5 - <1		Increase Medication	Decrease balloon volume Follow-up 12 and 20 weeks	Decrease balloon volume Follow-up 12 and 20 weeks	Decrease balloon volume Follow-up 12 and 20 weeks
	1 - <2			Decrease balloon volume Follow-up 8 and 16 weeks	Decrease balloon volume Follow-up 8 and 16 weeks	Decrease balloon volume Follow-up at 8 and 16 weeks*
	≥ 2				Remove Device	Remove Device*

\*Endoscopically Significant

All subjects in whom a gastric ulcer is confirmed will have endoscopic confirmation of complete healing 2-3 months after the balloon extraction.

Erosive gastritis, and Small Ulcers

Subjects with ulcers < 1 cm in diameter in all dimensions (< 0.5 cm is not considered an ulcer) and erosive gastritis should be treated with the following regimen: sucralfate 1,000 mg PO Qid and increasing PPI medication to twice daily for 3 months. A biopsy for H.pylori will be taken and treatment prescribed if positive. Balloon volume reduction at the discretion of the PI.

Endoscopic follow-up of these subjects prior to the 8-month extraction is not needed if they are asymptomatic. These subjects will not undergo adjustment at 18±4 weeks.

Non-Erosive Gastritis

If non-erosive gastritis is found at endoscopy, subjects will be treated with increasing PPI medication to twice daily for 2 months. A biopsy for H.pylori will be performed and treatment prescribed if positive.

Endoscopic follow up and healing confirmation (and H.pylori eradication, if positive) will be deferred until the adjustment endoscopy at week 18±4 weeks or extraction endoscopy at 8 months, whichever comes first (must be at least 2 months after this unscheduled endoscopy), unless symptomatic.

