### *4. 18- week adjustment*

At 18 weeks ± 4 weeks, all treatment arm subjects whose balloon has not been removed will be evaluated to determine if an upward adjustment is clinically appropriate. The following algorithm will be followed:

1. Subjects who have reached goal weight (calculated by BMI of 25) **and** are without any symptoms of gastroesophageal reflux or symptoms suggestive of gastritis or gastric ulcer, will not receive a balloon volume adjustment, and endoscopy at 18± 4 weeks will not be performed.
2. Subjects who underwent a prior unscheduled endoscopy with findings of a gastric ulcer will not receive an adjustment at 18± 4 weeks and no additional endoscopy beyond that described in section 2 above will be performed.
3. For all other subjects, endoscopy will be performed, and adjustments/treatment decisions will reflect the following algorithm:
  - a. For subjects with gastric ulceration found at endoscopy, **no upward adjustment** and PI will decide if balloon requires extraction based on endoscopic findings as described below.

Subjects who present with an endoscopically confirmed gastric ulcer will be treated as follows:

- **Ulcers whose smallest dimension (S) is  $\geq 2$ cm, or if there are any stigmata of increased risk of bleeding, such as visible vessels or clots**

The balloon should be extracted. Biopsy for H.pylori will be performed and treatment prescribed if positive.

These subjects should be treated with the following regimen: with sucralfate 1,000 mg PO Qid, and PPI medication twice daily for 3 months, followed by endoscopic evaluation after 3 months to confirm healing.

- **Ulcers whose smallest dimension (S) is  $\geq 1$  cm and  $< 2$  cm**

The balloon volume should be decreased by 150 ml (or 100 ml if starting volume is 400 ml) and subjects should be treated with the following regimen: sucralfate 1,000 mg PO Qid and increasing PPI medication to twice daily for 2 months. A biopsy for H.pylori will be taken and treatment prescribed if positive.

Endoscopic follow up will be performed at 8 weeks and if not healed at 8 weeks, an additional endoscopy at 16 weeks to confirm healing.

- At the 8-week follow-up, if signs of healing defined by a 25% reduction in either length or width are not observed, then the balloon should be extracted.

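### The ulcer text calls for balloon extraction when there are bleeding stigmata, but both summary tables and the small-ulcer rule omit that trigger

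*Combined protocol and SAP*

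**What the plan says.** Section 4.3.3.2.4 counts a gastric lesion as an ulcer from 5 mm in diameter, given unequivocal depth. Section 4.3.3.2.5 then sets out management twice: in item 2 (unscheduled endoscopy, under Gastric Ulceration) and in item 4 (18-week adjustment, step 3a). In both, the lead-in covers every confirmed ulcer: "Subjects who present with an endoscopically confirmed gastric ulcer will be treated as follows". The leading bullet calls for extraction when the smallest dimension S is at least 2 cm, "or if there are any stigmata of increased risk of bleeding, such as visible vessels or clots".

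Two further bullets assign a volume decrease by size. One covers S from 1 to under 2 cm. The other covers a largest dimension L of at least 1 cm with S under 1 cm.

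Each set of bullets is followed by a table introduced with "These recommendations are summarized in the following table". Its axes are L and S, and its only footnote marks endoscopically significant ulcers, a label that section 4.3.3.2.4 defines by size.

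After each table comes a separately headed rule for erosive gastritis and for ulcers under 1 cm in all dimensions. It prescribes sucralfate and twice-daily PPI. On the balloon it says "Balloon volume reduction at the discretion of the PI", and on follow-up "Endoscopic follow-up of these subjects prior to the 8-month extraction is not needed if they are asymptomatic".

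Step 2 of the 18-week algorithm adds that when an ulcer has already been found at an unscheduled endoscopy, "no additional endoscopy beyond that described in section 2 above will be performed".

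**The concern.** The stigmata limb is an alternative to the size limb, joined by an unrestricted 'or', under a lead-in that takes in every ulcer from 5 mm upward. The protocol does not state in so many words that it applies at any size, but that is the natural reading: a stigmata trigger confined to S of at least 2 cm would add nothing to the size criterion.

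The parts of the section most likely to be used at the bedside do not carry it. The tables sort by size alone. The small-ulcer rule has its own heading, follows the table and is more specific, so it can be read as displacing the general bullet. For a small ulcer with a visible vessel or clot, one rule takes the device out and the other leaves it in and waives the next look. At stake is a balloon left in place against a lesion that the protocol itself treats as being at increased risk of bleeding.

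**Working it through.** There is no planned figure to reproduce. The check compares the rules with each other and then works out the time to the next scheduled endoscopy.

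**Action for an ulcer with a visible vessel or clot** (same result in items 2 and 4 of section 4.3.3.2.5)

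| Ulcer size | Leading bullet | Table | Small-ulcer rule |
|---|---|---|---|
| 0.5 to under 1 cm in all dimensions | Extract | Increase medication | Medication; volume reduction optional |
| L ≥ 1 cm, S < 1 cm | Extract | Decrease volume; look at 12 and 20 weeks | Not covered |
| S 1 to < 2 cm | Extract | Decrease volume; look at 8 and 16 weeks | Not covered |
| S ≥ 2 cm | Extract | Remove | Not covered |

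Text and table differ in every size class below S = 2 cm.

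**Table cells.** Action cells by row of S: 4 (0–0.5 cm) + 4 (0.5 to < 1 cm) + 3 (1 to < 2 cm) + 2 (≥ 2 cm) = 13. Only the 2 cells with S ≥ 2 cm call for removal. The other 13 − 2 = 11 give a different action from the leading bullet if stigmata are present.

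**Next scheduled endoscopy, small asymptomatic ulcer.** Inputs: nominal explant at week 32 (section 3.3) and the 18 ± 4 week endoscopy, that is weeks 14 to 22. Gap = 32 − week found.

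- Found at the 18-week endoscopy: 32 − 22 = 10 weeks to 32 − 14 = 18 weeks.
- Found at an unscheduled endoscopy before week 14: step 2 removes the 18-week endoscopy, so the gap exceeds 32 − 14 = 18 weeks. Illustrative cases: week 4 gives 28 weeks, week 8 gives 24 weeks, week 13 gives 19 weeks.

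**Larger ulcers found at weeks 14 to 22, site following the table.**

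- 8-week rule: next look at 14 + 8 = week 22 to 22 + 8 = week 30, always before explant.
- 12-week rule: 14 + 12 = week 26 to 22 + 12 = week 34. Explant comes first when week found + 12 > 32, that is, for ulcers found after week 20.

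**The case against.** The strongest reply is that this is an omission and not a contradiction. The extraction rule heads both ulcer sections, and the tables sit directly beneath and are offered only as summaries. A two-way grid of dimensions cannot show a criterion that is not a dimension. No cell or sentence says to keep the balloon when stigmata are present, and a reader who applies the leading bullet first will extract. That stands for the two middle bullets, which the leading bullet naturally overrides. It also reduces the weight of the table point for larger ulcers, since an error there requires a site to use the table without the text above it. It does not dispose of the small-ulcer rule, which is separate, more specific and complete in itself.

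A second reply is that the intervals above apply to every small asymptomatic ulcer under a deliberate follow-up rule and are not produced by the missing words. This is correct. They show how long a missed extraction could go without a scheduled look; they do not measure how often one would occur.

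A third reply is that other safeguards exist:

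- visits with clinical assessment and adverse-event recording, every 4 weeks from week 4 to week 32 (section 4.3.4);
- unscheduled endoscopy at the investigator's discretion, and the investigator's decision on endoscopic findings at 18 weeks (section 4.3.3.2.5);
- standard of care for adverse events (section 6.2.3);
- committee review of ulcer rates with a stopping rule (sections 6.1 and 6.3.2);
- extraction for vomiting large amounts of blood (Table 1, section 6.2.2).

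These lower the risk, but none restores the trigger. The last acts only after bleeding. The 18-week decision refers the investigator to the rules below it, which include the same table and small-ulcer rule. On hemoglobin, "Blood hemoglobin will be monitored during scheduled or unscheduled endoscopies in patients who have ulcers or report signs of upper GI bleeding", so monitoring is tied to endoscopies that the small-ulcer rule waives.

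**Conclusion.** The concern holds. One extraction trigger is missing from two identical tables and from one small-ulcer rule stated in two places. The conflict is sharpest for ulcers under 1 cm, where two stated rules lead to opposite decisions about the device. For larger ulcers below S = 2 cm, the text is clear and the table is an incomplete summary of it.

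The conclusion rests on reading the stigmata limb as independent of size, and the intervals assume explant at week 32. The documents give no frequency of stigmata, so the number of subjects at risk cannot be estimated. Sample size, significance level and the method of the primary analysis are unaffected. Section 7.1.2 does treat an explanted subject as a dropout from that time, so consistent extraction decisions also keep that rule consistent across sites. This is a safety-procedure inconsistency that should be corrected; it does not put the validity of the trial in question.

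**What to change.** Carry the existing extraction rule through section 4.3.3.2.5, in both item 2 (unscheduled endoscopy) and item 4 (18-week adjustment):

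1. Footnote both tables: *Any ulcer with stigmata of bleeding risk: remove device regardless of size.*
2. Limit the small-ulcer rule to ulcers *without stigmata of bleeding*.
3. For clarity only, add the same limit to the two middle bullets.

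The cost is wording, made through a protocol amendment under section 10.2, submitted as appropriate to FDA and the IRBs, with notice to sites. No procedure, visit, data item or analysis is added.
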